13.1. Sample Size Considerations

Enrollment will continue until at least 30 RT-PCR confirmed positive subjects and 30 RT-PCR confirmed negative subjects have completed the study, with at least 3 low positives. In addition, at least 10 RT-PCR positive results should be from asymptomatic subjects and at least 30 subjects less than 14 years of age shall be included in the subject population.

Enrollment population must include subjects in the following age groups:

- <14 years of age, where the Parent or legal guardian collects a sample from their child (e.g., age 2-13) and performs the test
- 14-24 years of age
- 25-64 years of age
- ≥ 65 years of age

Current estimates of positive cases are approximately 8% of all-comers. Up to 600 subjects may be enrolled in this study. However, enrollment will be considered complete when the requirements for the study population have been met.

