The subjects will have a healthcare practitioner collect two nasal samples, one for the SOC testing and the second for the comparator test. The SOC sample will be used for patient management. Again, the results of the SOC will not be shared with the subject until the subject has interpreted the results from the Bio-Self COVID-19 Antigen Home Test. A minimum of 15 minutes will be required between each sample collection. The subject should be instructed to blow their nose prior to each sample collection. The comparator sample will be tested at a CLIA lab using the PerkinElmer New Coronavirus Nucleic Acid detection kit. Positive samples (RT-PCR and Bio-Self COVID-19 Antigen Home Test) will be sequenced by the CLIA lab. Once 30 sequence-confirmed omicron positive clinical samples have been identified, no further sequencing will be performed. Additionally, to ensure 10-20% of the samples are low positive, a cycle threshold (Ct) count will be performed for all RT-PCR positive samples. Low positives are defined as samples in which any gene target is within 3 Ct's of the mean Ct count of the RT-PCR comparator test's LoD. The following information will be collected and provided in the EUA application.

- specimen collection device
- specimen volume,
- eluate volume,

- specific extraction kit,
- extraction equipment,
- consumables
- platform.

Line data collection:

The original information and data for each subject will be collected in an excel spreadsheet including the following data elements for each specimen tested:

- Specimen type for the antigen test
- Specimen collection date and time for the antigen test
- Specimen testing date and time for the antigen test
- VTM type, as applicable, for the PCR
- Antigen test result with the reader
- Specimen type for RT-PCR
- Specimen collection date and time for RT-PCR test
- Specimen testing date and time for RT-PCR test
- Name of RT-PCR used as the comparator for each specimen
- RT-PCR test results (+/-)
- RT-PCR test value results (Ct values) for positive samples
- RT-PCR and Bio-Self COVID-19 Antigen Home Test positive samples sequencing, for the first 30 samples.
- Indicate if subject is asymptomatic or symptomatic. If symptomatic which of the following symptoms are they experiencing: Fever or chills, cough, shortness of breath or difficulty breathing, fatigue, muscle or body aches, headache, new loss of taste or smell, sore throat, congestion or runny nose, other-specify.

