- Number of days post-onset of patient symptoms
- Subject age, sex, race and ethnicity, if available.

7. Study Enrollment and Withdrawal

- 7.1. Study Population
 - 7.1.1.Enrollment population should represent different socioeconomic and educational backgrounds.
 - 7.1.2. High risk individuals should not be excluded from the study.
 - 7.1.3.Both symptomatic and asymptomatic individuals should be enrolled in the study.
 - 7.1.4. At least thirty (30) children ages of 2 13 should be enrolled in the study.
 - 7.1.5.Enrollment population must include subjects in the following age groups:
 - <14 years of age, where the Parent or legal guardian collects a sample from their child (e.g., ages 2-13) and performs the test
 - 14-24 years of age
 - 25-64 years of age
 - ≥ 65 years of age
 - 7.1.6. The first 50 subjects should be consecutively enrolled (i.e., in "all comers" style), including those who are either asymptomatic or symptomatic for COVID-19. Following the enrollment of the first 50 subjects, enroll only subjects who are symptomatic for COVID-19. When at least 30 RT-PCR confirmed positive specimens have been collected from symptomatic subjects, enrollment will continue with all comers, i.e., symptomatic and asymptomatic for COVID-19 until at least 10 RT-PCR confirmed positive specimens have been collected from asymptomatic subjects.
 - 7.1.7.A minimum of 30 symptomatic subjects testing positive and 30 subjects testing negative, confirmed by RT-PCR must be enrolled in the study.
 - 7.1.8. A minimum of 3 low positive samples.

- 7.1.9. A minimum of 10 asymptomatic subjects who test positive, confirmed by RT-PCR must be enrolled in the study.
- 7.1.10. Enrollment population will include any subject that presents for COVID-19 testing (both symptomatic and asymptomatic) that meets the eligibility criteria.
- 7.2. Subject Inclusion Criteria

To be enrolled in the study, the subject must meet all of the following inclusion criteria:

- 1. An Institutional Review Board (IRB) approved informed consent and assent, if applicable, is signed and dated prior to any study-related activities.
- 2. Male and female Subjects 2 years of age and older.
- 3. Subject is willing to provide a self-collected nasal swab sample. (If under the age of 14, the sample will be collected by an adult.)
- 4. Subject is willing to have nasal swabs collected by a healthcare professional.
- 5. Subject agrees to complete all aspects of the study.
- 7.3. Subject Exclusion Criteria

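### The minimum of 3 low positives in 7.1.8 and 13.1 is 7.5% of the 40 RT-PCR positives the plan requires, so it does not secure the 10-20% share set in the synopsis and 6.8

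*Combined protocol and SAP*

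**What the plan says.** The low-positive requirement appears in two forms.

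- **As a count.** Section 7.1.8 asks for "A minimum of 3 low positive samples". Section 13.1 carries the same number, enrolling "until at least 30 RT-PCR confirmed positive subjects and 30 RT-PCR confirmed negative subjects have completed the study, with at least 3 low positives".
- **As a share.** The Comparator text of 6.8 gives the aim as "to ensure 10-20% of the samples are low positive, a cycle threshold (Ct) count will be performed for all RT-PCR positive samples". The synopsis (Target Population/Sample Size) states the same 10-20% range, worded as a minimum. Its closing sentence attaches that range to the 30 symptomatic and 10 asymptomatic positive specimens.

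The number of positives is set in 7.1.7 ("A minimum of 30 symptomatic subjects testing positive and 30 subjects testing negative, confirmed by RT-PCR must be enrolled in the study") and 7.1.9 ("A minimum of 10 asymptomatic subjects who test positive, confirmed by RT-PCR must be enrolled in the study"). Section 13.1 gives 30 positives without symptom status and then says "In addition, at least 10 RT-PCR positive results should be from asymptomatic subjects".

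On completion, 13.1 ends: "However, enrollment will be considered complete when the requirements for the study population have been met". Study Population is the title of 7.1.

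**The concern.** A count and a percentage agree only at one denominator. The count of 3 fits the 30 positives named in the same sentence of 13.1, but the plan requires more than 30 positives. Section 7.1, the list that bears the name used in the completion rule, contains the count and no percentage. A site or statistician who closes enrollment against that list could stop with fewer low positives than the synopsis and 6.8 call for.

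The primary result is PPA, judged against a criterion of at least 80% in 13.2.2. Low positives are the specimens near the comparator's limit of detection, where an antigen test is most likely to miss. A minimum on their share guards against an easy specimen mix, so it should be a single rule that can be checked.

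**Working it through.** **Inputs from the documents.** Low-positive minimum 3 (7.1.8, 13.1). Share 10-20% (synopsis, 6.8). Symptomatic positives 30 and negatives 30 (7.1.7). Asymptomatic positives 10 (7.1.9). Positivity 8% of all-comers (13.1).

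**Reproducing the plan's figure.** 10% × 30 = 3. The stated minimum is therefore exactly the lower end of the range on a base of 30 positives. Three reaches 10% only while positives do not exceed 3/0.10 = 30.

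**Applying the required base.** 30 + 10 = 40 positives. Then 3/40 = 7.5%, while 10% × 40 = 4 and 20% × 40 = 8. The final all-comers stage in 7.1.6 can add further symptomatic positives. At assumed totals of 50 and 60, 3 is 6.0% and 5.0%, and 10% is 5 and 6.

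**Denominator.** Taking RT-PCR positives is an inference from the synopsis closing sentence and from 6.8, which measures Ct on the RT-PCR positives. The synopsis bullet speaks of clinical samples. If all samples were meant, the minimum of 40 positives and 30 negatives gives 3/70 = 4.3%, further below 10%.

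**How often the gap would appear.** Let X be binomial with n positives and low-positive probability p. The documents give no value for p, so a range is assumed. The gap is the event that X is at least 3 but below 10% of n.

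| n | Event | p = 10% | p = 15% | p = 20% |
|---|---|---|---|---|
| 40 | X = 3 | 0.200 | 0.082 | 0.021 |
| 50 (assumed) | X = 3 or 4 | 0.320 | 0.098 | 0.017 |
| 60 (assumed) | X = 3 to 5 | 0.384 | 0.093 | 0.012 |

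For n = 40 the first entry is C(40,3) × 0.1³ × 0.9³⁷ = 9880 × 0.001 × 0.0203 = 0.200. Each row assumes that enrollment stops at that total whatever the share.

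**The count of positives in 13.1.** If the 10 asymptomatic positives lie within the 30, then 20 symptomatic + 10 asymptomatic meets 13.1. If they are additional, the total is 40, but 30 of them still need not be symptomatic. Under 7.1.6, however, the rule after the first 50 subjects is "Following the enrollment of the first 50 subjects, enroll only subjects who are symptomatic for COVID-19", until 30 symptomatic positives are in hand. A stop that meets 13.1 but misses 7.1.7 would therefore need at least 10 asymptomatic positives among the first 50. At 8% positivity, the chance of at least 10 positives of any kind in 50 is 0.0056, which is an upper bound.

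**The case against.** The strongest reply is that the rules do not contradict each other. Both are minimums and can be met together. The synopsis lists the share among the things the enrolled population must include, and 6.8 gives Ct measurement as the means of ensuring it. A study that closed at 3 of 40 would therefore breach a stated requirement, and the problem arises only for someone who ignores those sections. It is true that there is no impossibility. But the completion rule points to the study population requirements, and 7.1, the section of that name, holds only the count. Measuring Ct shows the share; it does not by itself stop enrollment from closing too early.

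A second reply is that the shortfall at 40 positives is one specimen, which can move PPA by at most 1/40 = 2.5 percentage points, and that the assumed shares have no source in the documents. Both statements are correct, and they limit the weight of the point.

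Three stronger readings might be inferred and are not supported:

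- **That 4 to 7 low positives of 40 cannot be judged against the plan**, because the synopsis gives a range as a minimum. The synopsis wording is loose, but 4/40 = 10.0% and 7/40 = 17.5% lie inside the range in 6.8.
- **That enrollment could realistically close at 30 positives under 13.1.** Its closing sentence defers to the study population requirements, and the 7.1.6 sequence leaves a path of probability at most 0.006. Section 13.1 is looser than 7.1, not in conflict with it.
- **That a PPA calculation in the plan is wrong.** The mismatch is between enrollment minimums, not in an analysis formula.

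**Conclusion.** The point holds as a minor inconsistency. The count of 3 does not guarantee the plan's own share once the required 40 positives are used: it gives 7.5% against a lower limit of 10%, one specimen short, and the gap widens if more positives are enrolled. The 7.5% rests on documented counts and on the inferred denominator; the alternative denominator does not rescue the count. How likely the gap is depends on the assumed low-positive share: about one in five at 10% and small at 20%, for a stop at exactly 40. The different wording of the positives in 13.1 needs alignment only.

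**What to change.** In 7.1.8 and 13.1, replace the count of 3 with a minimum of 10% of all RT-PCR positives, rounded up: at least 4 of 40, 5 of 50 or 6 of 60. Use the same single minimum, with the denominator named, in the synopsis and 6.8 in place of the range. The sponsor may choose a higher value.

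As an alignment edit, have 13.1 state at least 30 symptomatic and at least 10 asymptomatic RT-PCR positives (at least 40 in total) and at least 30 negatives, matching 7.1.7 and 7.1.9.

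The alignment edit adds no subjects. The low-positive edit may need one or more extra low positives and slightly longer enrollment, because Ct is known only after testing. At assumed true shares of 10%, 15% and 20%, 40 positives contain at least 3 low positives with probability 78%, 95% and 99%, and at least 4 with probability 58%, 87% and 97%. A sponsor considering a 20% minimum should note that at least 8 of 40 would be reached with probability 4%, 24% and 56%.

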13.2. Statistical Methods

13.2.1. Performance Study - Sensitivity and Specificity

A 2 x 2 contingency table will be constructed as shown in Table 1 to display the frequencies of the Bio-Self COVID-19 Antigen Home Test and EUA SARS-CoV-2 RT-PCR test results, based on the positive and negative outcomes.

Table 1. Concordance of Bio-Self COVID-19 AntigenHome Test and the EUA SARS-CoV-2 RT-PCRcomparator assay			
Bio-Self COVID-19 Antigen Home	EUA SARS-CoV-2 RT-PCR Comparator Assay		
Test	Pos	Neg	Total
Pos	n_{11}	n ₁₂	n _{1.}
Neg	n ₂₁	n ₂₂	n _{2.}
Total	n .1	n _{.2}	n

Pos=positive, Neg=negative.

Based on the notation of Table 1, The sensitivity, specificity and 95% two-sided exact binomial confidence interval will be established.

The sensitivity is computed as the proportion of positive samples as called by the EUA SARS-CoV-2 RT-PCR assay, which are also positive as called by the Bio-Self COVID-19 Antigen Home Test; the sensitivity shall be computed as the ratio of $n_{11} / (n_{11} + n_{21})$.

The specificity is computed as the proportion of negative samples as called by the EUA SARS-CoV-2 RT-PCR assay, which are also negative as called by the Bio-Self COVID-19 Antigen Home Test; the specificity shall be computed as the ratio of $n_{22} / (n_{12} + n_{22})$.

13.2.2. Performance Study - Percent Agreement

A 2 x 2 contingency table will be constructed as shown in Table 1 to display the frequencies of the Bio-Self COVID-19 Antigen Home Test and EUA SARS-CoV-2 RT-PCR test results, based on the positive and negative outcomes.

Based on the notation of Table 1, The percent agreement and 95% two-sided exact binomial confidence interval will be established.

The overall percent agreement shall be computed as equal to 100% x $(n_{11} + n_{22})/(n_{11} + n_{12} + n_{21} + n_{22})$

The positive percent agreement (PPA) shall be computed as equal to 100% x $n_{11}/(n_{11} + n_{21})$

The negative percent agreement (NPA) shall be computed as equal to 100% x $n_{22}/(n_{12} + n_{22})$

Per FDA's Template for Developers of Molecular and Antigen Diagnostic COVID-19 Test for Home Use dated 11/09/2021, the following performance criteria will be used:

- NPA ≥98%
- PPA
 - For OTC single-use testing in all patient populations, including individuals with or without symptoms or other epidemiological reasons to suspect COVID-19: ≥ 80% PPA demonstrated in a clinical evaluation including both symptomatic and asymptomatic individuals;
 - For OTC testing in all patient populations, including individuals with or without symptoms or other epidemiological reasons to suspect COVID-19, with additional mitigations such as serial screening, as discussed in the "Supplemental Template for Developers of Molecular and Antigen Diagnostic COVID-19 Tests for Screening with Serial Testing"¹: ≥ 80% PPA with a lower bound (LB) of the two sided 95% confidence interval (CI) ≥70%, demonstrated

¹ Available at https://www.fda.gov/media/146695/download.

in a clinical evaluation including symptomatic individuals only or both symptomatic and asymptomatic individuals;

- For prescription home use single-use testing in individuals suspected of COVID-19 by their healthcare provider: ≥ 80% PPA demonstrated in a clinical evaluation including symptomatic individuals only (note that, for antigen tests, the indication may be limited to symptomatic individuals within a certain number of days of symptom onset, depending on the data); or
- For OTC single use testing in symptomatic individuals: ≥80% PPA demonstrated in a clinical evaluation including symptomatic individuals only (note that, for antigen tests, the indication may be limited to symptomatic individuals within a certain number of days of symptom onset, depending on the data).

14. Ethical Considerations

The investigator and site study staff will be responsible for the ethical conduct of this study in accordance with 45 CFR 46, 21 CFR 50, 21 CFR 56 governing IRB review and informed consent.

- 14.1. Institutional Review Board
 - 14.1.1. Each participating site must provide for review and approval of this protocol and associated informed consent by an appropriate IRB. Any amendments to the protocol or consent materials must also be reviewed and approved by the IRB prior to use.
 - 14.1.2. Prior to study initiation at each site, the Institutional Review Board (IRB) responsible for the studies to be conducted at each site or a central IRB must provide written approval of the protocol and informed consent. The investigator will provide IRB documentation for all applicable IRB submissions to the Sponsor. If IRB approval is withdrawn, the investigator will immediately report this to the Sponsor.
- 14.2. Informed Consent Process
 - 14.2.1. Informed consent is a process that is initiated prior to the Subject's agreement to participate in the study and continues throughout the study participation. The Principal Investigator must explain to each patient the nature of the clinical study, including any risks and benefits, its purpose and procedures, and expected duration of involvement in the clinical study. Each patient must be informed that participation in the clinical study is voluntary and non-participation will not affect his / her right to the most appropriate treatments or affect the doctor/clinician-patient relationship. Each patient must be given sufficient time to decide whether they wish to participate and have all their queries addressed prior to signing the IRB-approved consent form(s). A copy of the signed consent form(s) must be provided to the patient. Study specific procedures will not be initiated until the Subject has signed and dated the appropriate consent forms(s). Patients have full rights to withdraw from the clinical study at any time, irrespective of their initial consent.
 - 14.2.2. Each Subject must also give their permission for representatives of the Sponsor, auditor and regulatory authorities to review their hospital records for the purposes of source data verification.
 - 14.2.3. Written informed consent from the Subject must be obtained before any clinical investigation related procedures are performed.
- 14.3. Subject Confidentiality
 - 14.3.1. Confidentiality of Subject data will be maintained at all times. Subject anonymity will be guaranteed and all documentation relating to a Subject will be kept in a secure location.
 - 14.3.2. Study documents provided to the Sponsor will be stored in a secure location with access. None of the stored documents will contain any personal identifying information or direct identifiers.
 - 14.3.3. Study files will be made available to the IRB, regulatory authorities, Sponsor (or designee) and/or clinical study staff should they request access for auditing purposes.

15. Data Management

The investigator is responsible for ensuring the accuracy, completeness, legibility, and timeliness of the data reported. All data collection should be completed in a neat, legible manner to ensure accurate interpretation of data.

15.1. Data Management Responsibilities

Data collection and accurate documentation are the responsibility of the study staff under the supervision of the investigator. Data must be recorded using black ink and any changes or corrections made must be done by drawing a single line thru the original entry. The corrected entry must be initialed and dated by the individual making the corrections. **DO NOT ERASE, OVERWRITE, OR USE CORRECTION FLUID OR TAPE ON THE ORIGINAL**. The investigator or designee must review unanticipated problems.

15.2. Study Records Retention

The Principal Investigator will retain all copies of the records for a period of at least 2 years after the latter of the following two dates: the date on which the study is terminated or completed, or the date the declaration of emergency is rescinded. In all cases, the Principal Investigator must obtain written consent from the Sponsor prior to disposing of any records related to the clinical study.

16. Study Materials

- Bio-Self COVID-19 Antigen Home Test
- Bio-Self COVID-19 Antigen Home Test Quick Reference Instructions
- BioTeke Website

17. Literature References

- 1. Template for Developers of Molecular and Antigen Diagnostic COVID-19 Test for Home Use. Version November 9, 2021
- 2. Template for Developers of Antigen Tests. Version October 6, 2021
- 3. Supplemental Template for Developers of Molecular and Antigen Diagnostic COVID-19 Tests for Screening with Serial Testing. Version October 25, 2021

Version	Date	Section	Description of Change	Rationale
1.0	24 Mar 2022		Initial release	
2.0	05 May 2022	5. Synopsis; Study Design	Original: The order of testing will be 1) Subject self-collection, 2) standard of care (SOC) collection by a healthcare practitioner, and 3) comparator test collection by the healthcare practitioner. Revised to: The order of testing will be 1) standard of care (SOC) collection by a healthcare practitioner, 2) layperson conducts the test on themselves or another study participant using the Bio-Self Test, and 3) comparator test collection by the healthcare practitioner.	Additional input from FDA
2.0	05 May 2022	5. Synopsis; Target Population	Original: Subjects will be consecutively enrolled (i.e., in an "all comers" style) until at least 30 RT-PCR confirmed positive subjects and 30 RT-PCR confirmed negative subjects have completed the study. Revised to: The first 50 subjects will be consecutively enrolled (i.e., in an "all comers" style) including those who are either asymptomatic or symptomatic for COVID-19.	Clarification

18. Protocol Amendment History

			Following the enrollment of the first 50 subjects, enroll only subjects who are symptomatic for COVID-19. When at least 30 RT-PCR confirmed positive specimens have been collected from symptomatic subjects, enrollment will continue with all comers, i.e., symptomatic and asymptomatic for COVID- 19 until at least 10 RT-PCR confirmed positive specimens have been collected from asymptomatic subjects.	
2.0	05 May 2022	5. Synopsis; Target Population	Clarified enrollment population: At least 30 RT-PCR confirmed positive specimens collected from subjects that are symptomatic for COVID-19.	clarification
2.0	05 May 2022	5. Synopsis; Target Population	Original: Up to 600 subjects may be enrolled in this study to obtain a minimum of 30 RT- PCR confirmed positive subjects of which 10 subjects are asymptomatic and 10-20% are low positive. Revised to: Up to 600 subjects may be enrolled in this study to obtain a minimum of 30 RT-PCR confirmed positive specimens from subjects who are symptomatic, and 10 RT-PCR confirmed positive specimens from subjects who are asymptomatic for COVID-19	Clarification
2.0	05 May 2022	5. Synopsis; Site	with at least 10-20% being low positive. Revised the minimum of 3 testing locations to minimum of 2 testing locations	Administrative
2.0	05 May 2022	Requirements 6.8 Study Design	Revised the order of sample collection and added: To mitigate any potential bias which may affect the subject's visual interpretation of the Bio-Self COVID-19 Antigen Home Test result, the healthcare practitioner will not provide the SOC test results to the subject until after the results of the Bio-Self kit are read by the subject.	Additional input from FDA; clarification
2.0	05 May 2022	6.8 Study Design Comparator	Revised the order of collection and added the results of the SOC will not be shared with the subject until the subject has interpreted the results from the Bio-Self COVID-19 Antigen Home Test.	Additional input from FDA; clarification
2.0	05 May 2022	Section 7.1.6	Revised enrollment from all comers to: The first 50 subjects should be consecutively enrolled (i.e., in "all comers" style), including those who are either asymptomatic or symptomatic for COVID-19. Following the enrollment of the first 50 subjects, enroll only subjects who are symptomatic for COVID-19. When at least 30 RT-PCR confirmed positive specimens have been collected from symptomatic subjects, enrollment will continue with all comers, i.e., symptomatic and asymptomatic for COVID-19 until at least 10 RT-PCR confirmed positive specimens	Clarification

			have been collected from asymptomatic subjects.	
2.0	05 May 2022	Section 7.1.7	Added: Symptomatic to the 30 positive samples	Administrative
2.0	05 May 2022	Section 8.3	Revised the order of sample collection	Additional input from FDA
